### **Proportion of Patients Requiring Antibiotics**

The number and percentage of patients requiring antibiotics for influenza-related complications will be presented.

#### **4.3.1.1 Subgroup Analyses**

Subgroup analyses of the TTAS, based on virus type and subtype, may be conducted if there are a sufficient number of patients in each subgroup.

#### **4.3.2 Virology (Secondary) Endpoints**

The ITTi set will be used for all virology analyses.

For all virology analyses, baseline is defined as the last pre-dose assessment and where no pre-dose assessment is available baseline will be defined as the first post-dose assessment on Day 1. For nasal swab influenza hemagglutinin subtype, baseline is defined as the last pre-dose assessment and where no pre-dose assessment is available, baseline will be defined as the first post-dose assessment on Days 1–3.

### **Time to Cessation of Viral Shedding by Virus Titer**

Time to cessation of viral shedding by virus titer is defined as the time, in hours, between the initiation of any study treatment and first time when the influenza virus titer is below the limit of detection ( $0.75 \log_{10} \text{TCID}_{50}/\text{mL}$ ). Patients whose virus titers have not reached the limit by the last observation time point will be treated as censored at that time point. One day is converted into 24 hours.

Patients with a positive virus titer on Day 1 will be included in this analysis.

This endpoint will be summarized using descriptive statistics, as well as Kaplan-Meier plots.

### **Time to Cessation of Viral Shedding by RT-PCR**

Time to cessation of viral shedding by RT-PCR, in hours, is defined as the time between the initiation of study treatment and first time when the virus RNA by RT-PCR qualitative result is negative (no cycle threshold [Ct]-value detectable). Patients who do not have a negative result by the last observation time point will be treated as censored at that time point. For the patients with multiple virus types, this endpoint is defined as the time between the initiation of the study treatment and first time when the virus RNA by RT-PCR qualitative result is negative for all virus types. One day is converted into 24 hours.

Patients with a positive qualitative result on Day 1 will be included in this analysis.

This endpoint will be summarized using descriptive statistics, as well as Kaplan-Meier plots.

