## **2. STATISTICAL HYPOTHESES AND SAMPLE SIZE DETERMINATION**

### **2.1 STATISTICAL HYPOTHESES**

The primary objective of this study is to evaluate the safety of baloxavir marboxil in pediatric patients from birth to <1 year with influenza-like symptoms. Therefore, and as it is a single group study, there will be no formal statistical hypothesis testing.

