## **2.2 SAMPLE SIZE DETERMINATION**

No formal sample-size calculations have been performed.

A total of approximately 30 pediatric patients will be enrolled in order to estimate the PK parameters and maturation factor which is incorporated in the population PK model with a probability of >90%.

The number of patients in the intent-to-treat influenza-infected (ITTi) set will be monitored on an ongoing basis in order to ensure that an adequate number of influenza-infected patients are recruited. Additional patients may be recruited if the ITTi set is considerably smaller than expected.

The number of patients in the ITTi set entering the study with  $\leq 48$  hours since symptom onset will also be monitored. Additional patients may be recruited if considerably fewer patients than expected enter the study with  $\leq 48$  hours since symptom onset.

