## Appendix 2 Schedule of Activities (cont.)

Day(s)	Prescreening a	Treatment Period		Follow-Up Period										
		D1		D2	D3	D4	D5	D6	D7	D8	D9	D10	D15	D29 or ET
Visits	NA	V1 Screening	V1 Post-dose	V2	OpV1 b	V3		V4				V5	OpV2 b	V6
Visit Window (days)	NA					+1		+1				±2	±3	±3
Interview for meal consumption		x	x											
Clinical laboratory tests			x					x					(x i )	
Nasopharyngeal swabs k		x		x		x		x				x	(x i )	(x i )
Pharmacokinetic samples l			x	(x) l		(x) l						x l		
Palatability assessment m			x											

CARISS=Canadian Acute Respiratory Illness and Flu Scale; COVID-19 = coronavirus disease 2019; D=Day; ET=early termination; NA=not applicable; OpV=optional visit; PK=pharmacokinetic; V=visit.

- a Pre-screening assessment is not required if the patient has a negative COVID-19 test result and positive influenza test performed as SOC within 48 hours of screening recorded in their medical records.
- b OpV1 and OpV2 are optional visits to be performed at the discretion of the investigator or parent/caregiver, for example, in the event of persistent influenza symptoms.
- c Test is not required if the patient has a positive influenza test result performed as SOC within 48 hours of screening recorded in their medical records.
- d Test is not required if the patient has negative COVID-19 test results performed as SOC within 48 hours of screening recorded in their medical records.
- e Prior therapies will also be reviewed.
- f The parent/caregiver will assess and record in the patient diary, body temperature (tympanic assessment) four times daily (morning, noon, evening, and bedtime) on Days 1 to 3; twice daily (morning and evening) on Days 4 to 9; once daily on Days 10 to 15. The first temperature recorded by the parent/caregiver will be measured post-dose.
- g The parent/caregiver will complete the CARISS questionnaire twice (morning and evening) on Days 1 to 9 and then once daily on Days 10 to 15. The first CARISS assessment will occur post-dose.
- h Body weight and height will be measured on Days 1 and 29 only. Physical examinations on Days 2, 3, 4, 6, and 10 will be limited symptom – directed physical examinations and may be performed by a mobile nursing professional.

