## Appendix 2 Schedule of Activities (cont.)

- i Perform if the investigator determines that influenza symptoms are persisting or at the investigator's discretion.
- j Record vital sign measurements if abnormal physical examination, adverse events recorded since last visit, or at investigator's discretion on Day 29.
- k At least two nasopharyngeal swabs (one for each nostril) will be taken at each visit.
- l PK samples (all patients): See [Appendix 3](#) for collection timepoints for baloxavir marboxil and S-033447 concentration samples. Patients will be assigned to have either the Day 2 or the Day 4 sample. Only one sample from Days 6 to 10 is required and can be collected at either Visit 4 or Visit 5.
- m The palatability assessment should be completed by the study investigator (or delegate) who administers baloxavir marboxil to the patient.

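### Both viral-shedding Kaplan-Meier analyses run past Day 10 on swabs taken only for persisting symptoms or at discretion, so late censoring is potentially informative

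*SAP*

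**What the plan says.** SAP 4.3.2 defines time to cessation by RT-PCR as running from the start of treatment to the "first time when the virus RNA by RT-PCR qualitative result is negative", with no upper day limit. Its censoring rule is: "Patients who do not have a negative result by the last observation time point will be treated as censored at that time point". The titer endpoint has the same structure: "Patients whose virus titers have not reached the limit by the last observation time point will be treated as censored at that time point". Neither paragraph says whether the last observation is the last swab or the last study visit. Both endpoints are summarized with Kaplan-Meier plots, and SAP 4.3.1 adds medians for time-to-event endpoints.

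The row "Nasopharyngeal swabs" in the SAP Appendix 2 schedule has unconditional entries at screening and on Days 2, 4, 6 and 10. The entries at Optional Visit 2 (Day 15) and Visit 6 (Day 29 or early termination) are bracketed and carry footnote i: "Perform if the investigator determines that influenza symptoms are persisting or at the investigator's discretion". Under footnote b, Optional Visit 2 is itself at the choice of the investigator or the parent or caregiver, with persistent symptoms given as an example.

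SAP Table 2 brings the later swabs into the analysis data: Optional Visit 2 covers Days 12 to 22 and Visit 6 covers Day 23 onward. The change-from-baseline and proportion-positive virology endpoints, by contrast, are limited to Days 2, 4, 6 and 10.

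**The concern.** Kaplan-Meier estimation assumes that infants censored at a given time would have gone on to clear virus at the same rate as those still followed. Up to Day 10 the schedule supports this, because swabbing does not depend on how the infant is doing. After Day 10 it does not. An infant who is still positive but well may have no further swab and leave the risk set at about Day 10. An infant who is still positive and unwell is more likely to be swabbed on Day 15 or Day 29. From Day 10 on, the estimator applies the clearance of the swabbed infants to everyone still positive.

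At stake is the late part of two descriptive secondary curves and, if many infants are still RT-PCR positive at Day 10, the reported RT-PCR median. The SAP plans no sensitivity analysis for this and gives no caveat.

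**Working it through.** The documents give no figure for this endpoint in infants, so there is nothing to reproduce. The only cessation time they contain is the 24-hour median by titer in the adult and adolescent Phase III study (Protocol 1.2.3). They give none by RT-PCR.

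**Inputs.** The sample size comes from SAP 2.2: "A total of approximately 30 pediatric patients will be enrolled". The analyzed number can only be smaller, because these endpoints use influenza-infected infants who are positive on Day 1. The other inputs are assumptions:
- S10: share still RT-PCR positive at Day 10, varied from 0.1 to 0.7
- f: share of those who are swabbed later, set at 0.3
- cs, ca: probability of clearing by Day 15 in swabbed and unswabbed infants

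**Formulas for the share still shedding at Day 15.**
- If everyone were swabbed: S10 × (1 − [f·cs + (1 − f)·ca])
- Under the plan, censoring at the last swab: S10 × (1 − cs)
- Difference: S10 × (1 − f) × (ca − cs)

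Worked case with S10 = 0.7, cs = 0.4, ca = 0.7. Complete swabbing gives 0.7 × (1 − [0.12 + 0.49]) = 0.273. The plan gives 0.7 × 0.6 = 0.420. The difference is 0.7 × 0.7 × 0.3 = +0.147.

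| S10 | Complete (cs 0.4, ca 0.7) | Plan (cs 0.4, ca 0.7) | Difference | Difference, cs 0.3, ca 0.8 | Difference, cs = ca = 0.5 | Difference, cs 0.7, ca 0.4 |
|---|---|---|---|---|---|---|
| 0.1 | 0.039 | 0.060 | +0.021 | +0.035 | 0 | −0.021 |
| 0.3 | 0.117 | 0.180 | +0.063 | +0.105 | 0 | −0.063 |
| 0.5 | 0.195 | 0.300 | +0.105 | +0.175 | 0 | −0.105 |
| 0.6 | 0.234 | 0.360 | +0.126 | +0.210 | 0 | −0.126 |
| 0.7 | 0.273 | 0.420 | +0.147 | +0.245 | 0 | −0.147 |

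The sign is that of ca − cs. With no link between symptoms and clearance there is no bias. With a reverse link the tail is too short.

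**Infants behind the tail.** The expected number is 30 × S10 × f, which is 0.9 at S10 = 0.1 and 6.3 at S10 = 0.7.

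**Discretionary swabs.** If 30% of the remaining Day 10 positives were also swabbed, the swabbed share would be 0.3 + 0.7 × 0.3 = 0.51. Their average clearance would be (0.3 × 0.4 + 0.21 × 0.7)/0.51 = 0.524. At S10 = 0.7 the plan would give 0.7 × 0.476 = 0.333, a difference of +0.06 instead of +0.15.

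**Median.** If at most half are positive at Day 10, the median is reached by then and later swabs cannot alter it. A simulation with n = 30, 3,000 runs per setting, nominal swab times of 24, 72, 120, 216, 336 and 672 hours, and cs = 0.4, ca = 0.7 compared the planned median with the one under complete swabbing. The planned median was later in 0%, 0.1%, 6%, 17% and 29% of runs at S10 = 0.1, 0.3, 0.5, 0.6 and 0.7. At S10 = 0.7 with no link (cs = ca = 0.5) it was still later in 13% of runs and earlier in 1%, so part of the 29% comes from small numbers and not from bias.

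**Undefined last observation.** If it were read as the last study visit, unswabbed infants would count as still shedding after Day 10. The Day 15 value would be S10 × (1 − f·cs) = 0.7 × (1 − 0.12) = 0.616, against 0.273 with complete swabbing.

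**The case against.** The strongest reply is that the direction is not established. A reader might infer that late swabs come only from unwell infants and that the tail is therefore too long. Footnote i also allows swabs at discretion, and a caregiver can ask for Optional Visit 2. Nothing in the documents ties persisting symptoms to slower clearance. This stands: the size and sign above follow from assumed inputs.

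A reader might also infer that the RT-PCR median is distorted. That does not follow even from a strong contrast. Suppose 18 of 30 infants are positive at Day 10. Of these, 14 are not swabbed again and 12 of them clear by Day 15; 4 are swabbed and 1 clears. The plan gives 18/30 × 3/4 = 0.45, while the full count gives 5/30 = 0.167. Both fall below 0.5 at the Day 15 swab, so the median is the same. For titer, a median near the adult and adolescent 24 hours would leave few infants positive at Day 10 and little room for bias.

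These two endpoints are not uniquely open-ended either, since the virology AUC formulas also run to an unspecified last time. The study is single-arm and descriptive: "there will be no formal statistical hypothesis testing". No decision depends on these curves.

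Finally, a Day 10 cut-off discards observed clearances. In the simulation it left the median not reached in about 43%, 82% and 99% of runs at S10 = 0.5, 0.6 and 0.7. In those same settings, however, the planned median fell after Day 10 equally often and so came from the selected tail. These replies limit the consequence. They do not remove the dependence of late follow-up on clinical state.

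**Conclusion.** The point holds as a potential for informative censoring after Day 10. It is not a demonstrated bias in a known direction. The schedule makes late swabs depend on symptoms or discretion, and both shedding analyses use them without a cut-off. With f = 0.3, cs = 0.4 and ca = 0.7, the Day 15 estimate is about 0.02 to 0.15 too high for 10% to 70% still RT-PCR positive at Day 10. It is unbiased with no link and too low with a reverse link. In any of these cases the tail rests on roughly one to six infants of 30. The RT-PCR median is at risk only if about half or more remain positive at Day 10, which the documents give no means of judging. The titer endpoint is probably little affected. This is a cheap improvement to a descriptive secondary analysis, and it leaves the study's safety conclusions untouched.

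**What to change.** In both time-to-cessation paragraphs of SAP 4.3.2:

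1. Define the last observation as the last available swab result for that assay.
2. In the main analysis, censor infants not yet negative at the Visit 5 (Day 10) swab, or at their last earlier swab if Visit 5 is missing.
3. Where the curve has not fallen to 50%, report the median as not reached by Day 10.
4. Show Day 15 and Day 29 swabs in a listing, or in a sensitivity analysis that gives the number at risk and states that these swabs were selected on symptoms or discretion.

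An interval-censored (Turnbull) estimate, placing clearance between the last positive and first negative swab, is optional.

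The cost is SAP wording and minor programming, with no new data. Any median reached by Day 10 is unchanged. The downside is that the main curve ends at Day 10 and a later median is not estimated.

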### **Change from Baseline in Influenza Virus Titer at Each Timepoint**

Change from baseline in influenza virus titer ( $\log_{10}$ TCID50/mL) will be presented and is defined as the change from baseline in influenza virus titer on Days 2, 4, 6, and 10. If influenza virus titer is less than the lower limit of quantification, the virus titer will be imputed as 0.749 ( $\log_{10}$ TCID50/mL).

Only patients with a positive virus titer on Day 1 will be included in this analysis.

### **Change from Baseline in the Amount of Virus RNA (RT-PCR) at Each Timepoint**

Change from baseline in the amount of virus RNA (unit:  $\log_{10}$  vp/mL) will be presented and is defined as the change from baseline in the amount of virus RNA on Days 2, 4, 6, and 10.

If the amount of virus RNA is less than the lower limit of quantification, the amount of virus RNA will be imputed as the relevant LLOQ ( $\log_{10}$  vp/mL). If a patient is infected with multiple virus types, the sum of virus RNA ( $\log_{10}$  vp/mL) will be used for analysis.

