## **STATISTICAL ANALYSIS PLAN AMENDMENT RATIONALE**

Key changes from Version 2 to Version 3, along with the rationales for each change, are summarized below:

Section	Description of Change	Rationale for Change
Section 4.3.2	Clarified that the LLOQ will be used to impute the amount of virus RNA if less than the LLOQ. Added a table to specify the LLOQ for different assay versions.	Different assay versions have been introduced since the study start.
Section 4.4	Specify that if additional sequencing in PB1/PB2 is performed this may be reported in a CSR addendum.  Additional control virus data has been added for new lots.	Updated to clarify.  New lots have been added since study start.

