**Table 5 LLOQ for Different Assay Versions**

Influenza Type	Assay Version	LLOQ (log 10 vp/ml)
Influenza A	Version 1 50µl, 2014	2.18
	Version 1 20µl, 2019	2.48
	Version 2 20µl, 2023	2.79
Influenza B	Version 1 50µl, 2014	2.93
	Version 1 20µl, 2019	2.63

Patients with a positive by RT-PCR on Day 1 will be included in this analysis.

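### RNA below the limit is imputed at an assay-version floor (up to 0.61 log10 apart for flu A); the flu B limits move opposite to flu A without explanation, and the RNA AUC still uses the 2014 limits

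*SAP*

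**What the plan says.** SAP 4.3.2 presents change from baseline in virus RNA on Days 2, 4, 6 and 10. For a result under the lower limit of quantification (LLOQ), "the amount of virus RNA will be imputed as the relevant LLOQ".

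Table 5, headed "LLOQ for Different Assay Versions", lists the limits in log10 vp/mL:

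- Flu A: "Version 1 50µl, 2014 2.18"; "Version 1 20µl, 2019 2.48"; "Version 2 20µl, 2023 2.79".
- Flu B: "Version 1 50µl, 2014 2.93"; "Version 1 20µl, 2019 2.63". There is no Version 2 row.

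The SAP amendment rationale gives the reason for the table: "Different assay versions have been introduced since the study start".

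A later subsection of SAP 4.3.2, on the area under the curve in virus RNA, does not refer to Table 5. It gives one limit per virus type, 2.18 for flu A and 2.93 for flu B.

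The SAP plans no summary by assay version and no analysis of sensitivity to the floor. It also has no rule that all of one infant's samples be run on the same version.

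**The concern.** Three things in this part of the SAP do not sit well together.

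First, once a sample is below the limit, its change from baseline is simply the floor minus the baseline. If the floor depends on the assay, two infants with the same viral course get different falls because their samples were run on different versions. With about 30 infants planned, a few such samples can move a visit mean.

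Second, for the same assay version and the same change in volume, the flu A and flu B limits move by equal amounts in opposite directions, and the SAP does not say why. If a flu B limit is wrong, every flu B value imputed with it is wrong by the same amount.

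Third, the version-specific limits were not carried into the RNA AUC text, so the two RNA endpoints that use a quantitative floor may treat the same sample differently.

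**Working it through.** **Inputs.** The five limits come from Table 5, and the AUC limits (2.18 and 2.93) from the RNA AUC subsection of SAP 4.3.2. The documents give no formula or validation data for an LLOQ, so there is no plan figure to reproduce. They also give no baseline RNA for this population; baselines of 5 to 8 log10 vp/mL are assumed below.

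**1. Spread between versions.**
- Flu A: 2.48 − 2.18 = 0.30; 2.79 − 2.48 = 0.31; 2.79 − 2.18 = 0.61. On the natural scale 10^0.61 = 4.1-fold, about 151 against 617 vp/mL.
- Flu B: 2.63 − 2.93 = −0.30, and 10^0.30 = 2.0-fold.

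**2. Change recorded for a below-limit sample** (limit minus assumed baseline):

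| Assumed baseline | A, 50 µl 2014 | A, 20 µl 2019 | A, Version 2 2023 | B, 50 µl 2014 | B, 20 µl 2019 |
|---|---|---|---|---|---|
| 5 | −2.82 | −2.52 | −2.21 | −2.07 | −2.37 |
| 6 | −3.82 | −3.52 | −3.21 | −3.07 | −3.37 |
| 7 | −4.82 | −4.52 | −4.21 | −4.07 | −4.37 |
| 8 | −5.82 | −5.52 | −5.21 | −5.07 | −5.37 |

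The gap between versions does not depend on the baseline. Relative to the largest measurable flu A fall, 0.61/(baseline − 2.18) is 22%, 16%, 13% and 10% at baselines of 5, 6, 7 and 8.

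**3. Effect on a mean.** Suppose a share s of the below-limit flu A samples at a visit were run on the 2023 version and the rest on the 2014 version. Compared with all on the 2014 version, their mean change shifts by 0.61 × s: 0.15 at s = 25%, 0.31 at 50%, 0.46 at 75%. If only a fraction p of all flu A samples at that visit is below the limit, the shift in the flu A mean is 0.61 × s × p, for example 0.61 × 0.5 × 0.5 = 0.15. Neither s nor p is in the documents.

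**4. Direction of the flu B step.** From 50 µl (2014) to 20 µl (2019), both labelled Version 1, flu A moves +0.30 and flu B −0.30. If the volume is sample input and nothing else changed, a per-mL limit would rise by log10(50/20) = 0.40. Flu B goes the other way, but flu A does not match 0.40 either. The value 2.63 appears only in Table 5; 2.93 also appears in the AUC subsection.

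**5. AUC limits against Table 5.** Table 5 minus the AUC limit is 0, 0.30 and 0.61 for the three flu A versions, and 0 and −0.30 for the two flu B versions. For a Version 2 flu A sample, 2.18 lies 0.61 below what Table 5 says that assay can quantify. For a 20 µl flu B sample, 2.93 lies 0.30 above it, so a quantified result between 2.63 and 2.93 would fall under the AUC limit. As an illustration, an infant with flu A below the limit from Day 4 to Day 10 (6 days) would differ by 0.61 × 6 = 3.66 log10·days over that stretch, depending on whether 2.18 or 2.79 is used.

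**The case against.** The strongest reply is that the version-specific floor is deliberate and defensible: each sample is imputed at the limit of the assay that measured it. A common floor at the highest limit would replace some properly quantified values with a constant. That stands, and it is why the common floor belongs in a sensitivity analysis and not in place of the specified rule.

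The reach is also limited. Safety is primary, and virology is secondary and descriptive with no hypothesis test. Virus titer endpoints use a single limit of 0.75 log10 TCID50/mL. RNA shedding time and RNA positivity use the qualitative result, so Table 5 does not enter them. The full 0.61 needs below-limit flu A samples from both the 2014 and the 2023 versions. All of this stands.

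Three stronger readings are tempting, and the documents do not support them.

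- *The flu B rows are transposed, or 2.63 should be 3.23 (2.93 + 0.30).* The AUC subsection pairs 2.18 with 2.93, the same pair that Table 5 lists for 2014, which speaks against a swap. The SAP does not say what the volumes measure, and a limit can be set by validation and not by volume alone. The value 3.23 appears nowhere.
- *Most infants are below the limit at later visits, so the summary is mainly floor.* The documents give no such share. In the Japanese pediatric study described in Protocol 1.2.4, the mean RNA change on Day 2 was −1.75 log10, against −4.20 for titer, so on Day 2 at least RNA fell much less than the fully cleared examples above. Later visits are unknown.
- *The absent flu B Version 2 row is an omission.* Version 2 may not have been used for flu B. The SAP should say so, but an error is not shown.

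**Conclusion.** The point holds as a matter of imputation and consistency, not as a proven wrong number. A below-limit sample's RNA change from baseline depends on assay version by up to 0.61 log10 for flu A (0.30 or 0.31 between adjacent versions) and by 0.30 for flu B. These gaps follow from the SAP's rule and table alone. Their effect on the reported means depends on the share of below-limit samples per version, which is not given.

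The opposite flu B step is unexplained and warrants a check; the documents cannot settle which flu B value, if either, is wrong. The AUC text is the firmest inconsistency: it keeps the 2014 limits whatever the version, so one sample can carry floors that differ by 0.30 or 0.61 (flu A) or 0.30 (flu B) across two RNA endpoints. This assumes that the limit stated there serves as the AUC floor, since that subsection does not spell out the imputation.

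No error rate or sample size is affected. The matter is worth correcting before lock because it is cheap and because assay differences would otherwise appear as differences in viral decline.

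**What to change.** Before database lock:

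1. Verify both flu B rows of Table 5 against the assay validation reports, and correct them if needed. State whether Version 2 was used for flu B and, if it was, add its limit.
2. Replace the fixed 2.18 and 2.93 in the RNA AUC subsection with a reference to Table 5, and state there that below-limit values take the version-specific limit, so that both RNA endpoints use the same floor.
3. Keep the version-specific floor as the main rule. Add a sensitivity analysis of RNA change from baseline and RNA AUC with one common floor per virus type: the highest LLOQ of any version actually used for that type, with every value below it set to it.
4. Report the number of samples, and the number below the limit, by assay version and visit, so that a reader can judge how much the floor matters.

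The cost is one document check, a few lines of SAP text and some extra output. In the sensitivity analysis, some low but quantified values from the more sensitive versions lose resolution; the main analysis keeps them.

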#### **Area under the Curve in Virus Titer**

Area under the concentration–time curve (AUC) in virus titer will be presented and will be calculated using the trapezoidal method. AUC change from time 0 (t0) to time K (tK) is given by the formula:

$$\sum_{k=1}^K \frac{(y_k + y_{k-1})(t_k - t_{k-1})}{2}$$

where tk (hours) represents the date of the kth viral titer assessment (k=0, ..., K) and yk represents the log10 value of the kth viral titer assessment (TCID50/mL).

Twenty-four hours of time will be converted into one day. Patients with a positive virus titer on Day 1 will be included in this analysis. The lower limit of quantification and lower limit of detection is defined as 0.75 log10TCID50/mL for flu A and 0.75 log10TCID50/mL for flu B. If a patient is infected with multiple virus types, the sum of those virus titers will be used for analysis.

Additionally, the AUC in virus titer adjusted for baseline will be presented and will be calculated using the trapezoidal method. AUC of change from baseline from time 0 ( $t_0$ ) to time K ( $t_K$ ) is given by the formula

$$\sum_{k=1}^K \frac{(y_k + y_{k-1} - 2y_0)(t_k - t_{k-1})}{2}$$

where  $t_k$  (hours) represents the date of the  $k^{\text{th}}$  viral titer assessment ( $k = 0, \dots, K$ ) and  $y_k$  represents the  $\log_{10}$  value of the  $k^{\text{th}}$  viral titer assessment (TCID50/mL).

Twenty-four hours will be converted into one day. Patients with a positive virus titer on Day 1 will be subjected to this analysis. The lower limit is defined as 0.75 log10TCID50/mL for flu A and 0.75 log10TCID50/mL for flu B. If a patient is infected with multiple virus types, the sum of virus titers (TCID50/mL) will be used for analysis.

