### **Area under the Curve in the Amount of Virus RNA (RT-PCR)**

Area under the concentration–time curve (AUC) in virus RNA (RT-PCR) will be presented and is defined as AUC of change from baseline in the amount of virus RNA (RT-PCR). AUC is calculated using the trapezoidal method similar to AUC in virus titer. Patients with a positive RT-PCR result on Day 1 will be subjected to this analysis. The lower limit of quantification is defined as 2.18 for flu A and 2.93 for flu B (log10 vp/mL). If a patient is infected with multiple virus types, the sum of those the amount of virus RNA will be used for analysis.

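### Read as written, the SAP adds log10 RNA values across virus types, which can overstate a dual-type infant's fall by up to about a factor of two; the multi-type rules need one stated scale

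*SAP*

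**What the plan says.** All of the rules below are in SAP Section 4.3.2.

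- **Change from baseline in virus RNA.** The endpoint is in log10 vp/mL, on Days 2, 4, 6 and 10. Below the quantification limit, "the amount of virus RNA will be imputed as the relevant LLOQ", also in log10 vp/mL, with limits by assay version in Table 5. The next sentence begins "If a patient is infected with multiple virus types, the sum of virus RNA" and puts log10 vp/mL in brackets as the unit. Nothing says that values are converted to vp/mL before they are added.
- **AUC in virus RNA.** For multiple types, "the sum of those the amount of virus RNA will be used for analysis". No unit is attached to this sum. The log10 unit in that paragraph belongs to the preceding sentence on limits ("The lower limit of quantification is defined as 2.18 for flu A and 2.93 for flu B").
- **AUC in virus titer.** The rule appears twice. Beside the unadjusted formula, which uses log10 titers, it reads "If a patient is infected with multiple virus types, the sum of those virus titers will be used for analysis", with no unit. Beside the baseline-adjusted formula it reads "the sum of virus titers (TCID 50 /mL) will be used for analysis", which is the natural scale.
- **Change from baseline in virus titer.** There is no rule for multiple types.
- **RT-PCR endpoints that are not amounts.** Time to cessation requires a negative result for every type. The proportion positive uses the qualitative result.

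Neither document gives an expected number of infants with two influenza types, or their viral loads.

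**The concern.** A programmer who holds one log10 value per type and follows the RNA change paragraph would add the two values. That sum is the log of the product of the loads. It is not a viral load on the scale used for every single-type infant in the same table.

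On that reading a dual-type infant's baseline, lowest reportable value and change from baseline would all be inflated. An infant with both viruses below quantification would be shown above 5 log10 vp/mL, while the fall from baseline could be about twice the fall in total RNA. With about 30 infants and descriptive summaries, one such value could be the extreme of the range.

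Even if the total load was intended, the rules name log10 in one place, the natural scale in another and no scale in two more. Two programmers could follow the SAP and report different numbers.

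**Working it through.** The plan attaches no figure to this rule, so there is nothing to reproduce. The check compares the two readings.

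**Inputs**
- Limits from SAP Table 5 (log10 vp/mL): flu A 2.18 (2014), 2.48 (2019), 2.79 (2023, listed as "Version 2 20µl, 2023"); flu B 2.93 (2014), 2.63 (2019).
- For scale, the mean Day 2 RNA change in the earlier Japanese pediatric study was -1.75 log10 (Protocol Section 1.2.4).
- Planned enrolment is about 30 (SAP Section 2.2).
- **Assumption:** baseline loads per type in a dual-type infant. The examples use 3 to 7 log10 vp/mL.

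**Formulas.** Let a and b be the log10 loads of the two types.
- Literal reading: S = a + b = log10(A × B).
- Total load: T = log10(10^a + 10^b).
- Change = post-dose value minus baseline.

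**1. Both types fall by d.** S changes by -2d. T changes by -d, because 10^-d factors out of the sum. The ratio is exactly 2: with d = 1.75, -3.50 against -1.75.

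**2. Floor, both types below the limit**
- 2014: 2.18 + 2.93 = 5.11, against log10(10^2.18 + 10^2.93) = 3.00.
- 2019: 2.48 + 2.63 = 5.11, against 2.86.
- A 2023 with B 2019: 2.79 + 2.63 = 5.42, against 3.02.

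**3. Both types fall to the limit.** For baselines 7 and 6, S goes from 13.00 to 5.11, and T starts at log10(10^7 + 10^6) = 7.04.

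| Assumed baseline A/B | Limits | Change in S | Change in T | Ratio |
|---|---|---|---|---|
| 6/6 | 2014 | -6.89 | -3.30 | 2.09 |
| 6/6 | 2019 | -6.89 | -3.44 | 2.00 |
| 7/6 | 2014 | -7.89 | -4.04 | 1.95 |
| 7/6 | 2019 | -7.89 | -4.18 | 1.89 |
| 6/5 | 2014 | -5.89 | -3.04 | 1.94 |
| 7/5 | 2014 | -6.89 | -4.00 | 1.72 |
| 7/4 | 2014 | -5.89 | -4.00 | 1.47 |
| 7/4 | 2019 | -5.89 | -4.14 | 1.42 |
| 7/3 | 2014 | -4.89 | -4.00 | 1.22 |

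**4. Only the dominant virus falls, 7/4 to 4/4.** S: 11 to 8 = -3.00. T: 7.00 to 4.30 = -2.70. Ratio 1.11.

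The range 1.1 to about 2 covers these patterns. It is not a bound. If one of two equal viruses persists (6/6 to 4/6), S changes by -2.00 and T by only -0.30. The ratio is then large, but the excess is 1.70 log10, about the same as in step 1.

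**5. Effect of one such infant on a mean of 30 (excess ÷ 30)**
- Both types fall by 1.75: 1.75/30 = 0.06.
- 7/6 to the limit: 3.71/30 = 0.12 (2019) or 3.85/30 = 0.13 (2014).
- Only the dominant virus falls: 0.30/30 = 0.01.

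If every infant truly falls by 1.75, one, two or three dual-type infants among 30 move the reported mean to -1.81, -1.87 or -1.93.

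**6. RNA AUC.** It is defined as the AUC of change from baseline. The trapezoidal sum is linear in those changes, so doubling the change at every visit doubles the AUC. This applies only if the log-scale sum is used there, which the text does not state.

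**The case against.** The strongest objection is that this is loose wording and not a wrong method. The SAP never instructs anyone to add log10 values. The bracket could label the unit of the result, meaning total RNA reported in log10 vp/mL, and the titer rule in TCID50/mL suggests that a total load was intended. That reading is possible. The SAP's own usage weighs against it: beside the baseline-adjusted titer formula, which is in log10, the bracket names the scale on which values are added, and the bracket after the RNA limit names the scale of the value itself. Neither point is decisive, and the scale remains unstated or inconsistent on any reading.

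A reader might also infer more than the documents support:
- **That RNA AUC is certainly wrong.** Its multi-type sum has no unit, so the effect there is conditional.
- **That virology is affected throughout.** Time to cessation by RT-PCR has a sound multi-type rule, and the proportion positive by RT-PCR is qualitative. Neither is touched.
- **That near-doubling is typical.** It needs equal falls, or similar baselines with both types reaching the limit. When one virus dominates, the ratio is about 1.1 to 1.5 in most of the examples.
- **That trial conclusions are at risk.** The endpoints are secondary, there is no formal hypothesis test (SAP Section 2.1), a median would be little moved by one infant, and there may be no dual-type infant at all.

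These limits hold. They reduce the size and certainty of the point but do not remove the need to state the scale.

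**Conclusion.** The point stands as a defect in a stated derivation rule, with limited reach. As written, the RNA change rule adds log10 values; the intended rule may differ, but the SAP does not say so.

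On the literal reading, change from baseline in RNA is wrong for any dual-type infant, and RNA AUC is wrong if it uses the same sum. The size rests on assumed loads: a factor of about 1.1 to about 2 in the patterns described, with a floor of 5.11 log10 instead of 3.00 or 2.86. The shift of 0.06 to 0.13 log10 assumes that all 30 infants contribute to the mean and that both types fall; it is smaller when only the dominant virus falls. An individual value, and therefore the range, can be badly distorted even where the mean barely moves. No error rate or sample size depends on it.

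**What to change.** State one rule in the paragraphs on change from baseline in RNA, AUC in virus titer (both places) and AUC in virus RNA. Add it to the paragraph on change from baseline in titer, which has no multi-type rule:

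> For patients with multiple virus types, after imputation of values below the LLOQ, convert each type to vp/mL (or TCID50/mL), add on that scale, then take log10 of the sum, at baseline and at every visit.

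The second titer AUC rule already names the natural scale and needs only to be aligned. The cost is one sentence in four SAP paragraphs and one line of derivation code. No new data are needed. The change is best made before database lock, so that the scale is fixed before the values are derived.
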